3.1 Eligibility Criteria

3.1.1 Participants must have histologically confirmed solid tumor malignancy that is metastatic or unresectable and for which standard curative or palliative measures do not exist or are no longer effective. Participants with uncontrolled Kaposi sarcoma are permitted (KS must be increasing despite HAART and HIV suppression for greater than or equal to 2 months, or stable KS despite HAART for greater than or equal to 3 months).

For participants in the 24-participant solid tumor cohort, only those histologies not known to respond to single agent nivolumab (such as pancreas, prostate, and MSS colorectal cancer) will be excluded.

For participants in the relapsed refractory HIV-cHL expansion cohort, participants must have histologically confirmed, relapsed/refractory (defined as relapsed/refractory to one or greater lines of therapy) HIV-associated classical HL.

- 3.1.2 HIV-1 infection, as documented by any federally approved, licensed HIV rapid test performed in conjunction with screening (or ELISA, test kit, and confirmed by Western blot or other approved test). Alternatively, this documentation may include a record demonstrating that another physician has documented the participant's HIV status based on either: 1) approved diagnostic tests, or 2) the referring physician's written record that HIV infection was documented, with supporting information on the participant's relevant medical history and/or current management of HIV infection.
- 3.1.3 Participants must have measurable disease, defined as at least one lesion that can be accurately measured in at least one dimension (longest diameter to be recorded for non-nodal lesions and short axis for nodal lesions) as ≥20 mm with conventional techniques or as ≥10 mm with spiral CT scan, MRI, or calipers by clinical exam. Scans must have been performed within 4 weeks prior to registration. See Section 9.1.3 or Section 9.3 for HL for the evaluation of measurable disease. Note: For participants with Kaposi sarcoma, the following apply: At least five measurable cutaneous KS lesions or any number of lesions with systemic unresectable disease

with no previous local radiation, surgical, or intralesional cytotoxic therapy that would prevent response assessment.

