9.1.1 Definitions

Evaluable for Toxicity: All participants will be evaluable for toxicity from the time of their first treatment with nivolumab and/or ipilimumab.

Evaluable for Objective Response: Only those participants who have measurable disease present at baseline, have received at least one cycle of therapy, and have had their disease re-evaluated will be considered evaluable for response. These participants will have their response classified according to the definitions stated below. (Note: Participants who exhibit objective disease progression prior to the end of cycle 1 will also be considered evaluable.)

Evaluable Non-Target Disease Response: Participants who have lesions present at baseline that are evaluable but do not meet the definitions of measurable disease, have received at least one cycle of therapy, and have had their disease re-evaluated will be considered evaluable for non-target disease. The response assessment is based on the presence, absence, or unequivocal progression of the lesions.

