9.1.2 Disease Parameters

Measurable Disease: Measurable lesions are defined as those that can be accurately measured in at least one dimension (longest diameter to be recorded) as \geq 20 mm

by chest x-ray, as ≥ 10 mm with CT scan, or ≥ 10 mm with calipers by clinical exam. All tumor measurements must be recorded in millimeters (or decimal fractions of centimeters).

Note: Tumor lesions that are situated in a previously irradiated area might or might not be considered measurable. Such lesions should be considered measurable only if evidence of disease progression has been observed in this site. Disease present only in a previously irradiated field should have biopsy confirmation.

Malignant Lymph Nodes: To be considered pathologically enlarged and measurable, a lymph node must be ≥ 15 mm in short axis when assessed by CT scan (CT scan slice thickness recommended to be no greater than 5 mm). At baseline and in follow-up, only the short axis will be measured and followed.

Non-measurable Disease: All other lesions (or sites of disease), including small lesions (longest diameter <10 mm or pathological lymph nodes with ≥ 10 to <15 mm short axis), are considered non-measurable disease. Bone lesions, leptomeningeal disease, ascites, pleural/pericardial effusions, lymphangitis cutis/pulmonitis, inflammatory breast disease, and abdominal masses (not followed by CT or MRI), are considered as non-measurable.

Note: Cystic lesions that meet the criteria for radiographically defined simple cysts should not be considered as malignant lesions (neither measurable nor non-measurable) since they are, by definition, simple cysts.

'Cystic lesions' thought to represent cystic metastases can be considered as measurable lesions, if they meet the definition of measurability described above. However, if non-cystic lesions are present in the same participant, these are preferred for selection as target lesions.

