9.1.3 Methods for Evaluation of Measurable Disease

All measurements should be taken and recorded in metric notation using a ruler or calipers. All baseline evaluations should be performed as closely as possible to the beginning of treatment and never more than 4 weeks before the beginning of the treatment.

The same method of assessment and the same technique should be used to characterize each identified and reported lesion at baseline and during follow-up. Imaging-based evaluation is preferred to evaluation by clinical examination unless the lesion(s) being followed cannot be imaged but are assessable by clinical exam.

Clinical Lesions: Clinical lesions will only be considered measurable when they are superficial (e.g., skin nodules and palpable lymph nodes) and ≥ 10 mm diameter as assessed using calipers (e.g., skin nodules). In the case of skin lesions, documentation by color photography, including a ruler to estimate the size of the lesion, is recommended.

Chest X-ray: Lesions on chest x-ray are acceptable as measurable lesions when they are clearly defined and surrounded by aerated lung. However, CT is preferable.

Conventional CT and MRI: This guideline has defined measurability of lesions on CT scan based on the assumption that CT slice thickness is 5 mm or less. If CT scans have slice thickness greater than 5 mm, the minimum size for a measurable lesion should be twice the slice thickness. MRI is also acceptable in certain situations (e.g. for body scans).

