9.1.4 Response Criteria

9.1.4.1 Evaluation of Target Lesions

Complete Response (CR): Disappearance of all target lesions. Any pathological lymph nodes (whether target or non-target) must have reduction in short axis to <10 mm.

Partial Response (PR): At least a 30% decrease in the sum of the diameters of target lesions, taking as reference the baseline sum diameters

Progressive Disease (PD): At least a 20% increase in the sum of the diameters of target lesions, taking as reference the smallest sum on study (this includes the baseline sum if that is the smallest on study). In addition to the relative increase of 20%, the sum must also demonstrate an absolute increase of at least 5 mm. (Note: the appearance of one or more new lesions is also considered progressions).

Stable Disease (SD): Neither sufficient shrinkage to qualify for PR nor sufficient increase to qualify for PD, taking as reference the smallest sum diameters while on study

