IV contrast should be used for all CT scans. If IV contrast is contraindicated, CT may be performed without contrast. Alternatively, MRI can be used to assess lesions in the participant. Participants who develop contrast allergy after study enrollment may be followed by MRI for subsequent tumor measurements. Sections should be contiguous, similarly sized and consistent from visit-to-visit. Section thickness must be based on institutional standards (e.g., from 5 to 8 mm; 10 mm cuts are not recommended). Chest x-ray, ultrasound, and PET scans are not acceptable methods to measure disease for the purposes of this study.

APPENDIX X: NIVOLUMAB: MANAGEMENT ALGORITHMS FOR ENDOCRINOPATHY, GASTROINTESTINAL, HEPATIC, NEUROLOGICAL, PULMONARY, RENAL, AND SKIN ADVERSE EVENTS

Management algorithms for the above-mentioned AEs are provided on the following pages.

[figure not shown]
Endocrinopathy Management Algorithm

Rule out non-inflammatory causes. If non-inflammatory cause, treat accordingly and continue immuno-oncology (I-O) therapy. Consider visual field testing, endocrinology consultation, and imaging.

[figure not shown]
GI Adverse Event Management Algorithm

Rule out non-inflammatory causes. If non-inflammatory cause is identified, treat accordingly and continue I-O therapy. Opiates/narcotics may mask symptoms of perforation. Infliximab should not be used in cases of perforation or sepsis.

Hepatic Adverse Event Management Algorithm

Rule out non-inflammatory causes. If non-inflammatory cause, treat accordingly and continue I-O therapy. Consider imaging for obstruction.

[figure not shown]

^{*}I-O therapy may be delayed rather than discontinued if AST/ALT ≤ 8 x ULN and T.bili ≤ 5 x ULN.

^{**}The recommended starting dose for grade 4 hepatitis is 2 mg/kg/day methylprednisolone IV.

[figure not shown]
Neurological Adverse Event Management Algorithm

Rule out non-inflammatory causes. If non-inflammatory cause, treat accordingly and continue I-O therapy.

[figure not shown]
Pulmonary Adverse Event Management Algorithm

Rule out non-inflammatory causes. If non-inflammatory cause, treat accordingly and continue I-O therapy. Evaluate with imaging and pulmonary consultation.

[figure not shown]
Renal Adverse Event Management Algorithm

Rule out non-inflammatory causes. If non-inflammatory cause, treat accordingly and continue I-O therapy

Skin Adverse Event Management Algorithm

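### For RECIST-assessed solid tumors, the entry criterion counts a 10 mm short-axis node as measurable, but Section 9.1.2 requires 15 mm, so a node-only participant can be enrolled as measurable and yet not be evaluable for objective response

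*Combined protocol and SAP*

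**What the plan says.** - **Entry (3.1.3).** Measurable disease is at least one lesion measured by longest diameter if non-nodal, or by "short axis for nodal lesions) as ≥20 mm with conventional techniques or as ≥10 mm with spiral CT scan, MRI, or calipers". Nodes thus get the same 10 mm cut-off as other lesions. For detail the criterion says "See Section 9.1.3 or Section 9.3 for HL for the evaluation of measurable disease". Kaposi sarcoma has a separate note.
- **Response (9.1.2).** To count as measurable, "a lymph node must be ≥ 15 mm in short axis when assessed by CT scan". The same section says that "pathological lymph nodes with ≥ 10 to <15 mm short axis), are considered non-measurable disease". Target lesions are chosen from the measurable lesions.
- **Evaluability (9.1.1).** "Only those participants who have measurable disease present at baseline", who have also had at least one cycle and a re-evaluation, are evaluable for objective response. Participants with only non-measurable lesions fall in a separate non-target category, scored by Table 5.
- **Complete response (9.1.4.1, 9.1.4.2).** Pathological nodes, target or not, "must have reduction in short axis to <10 mm". The non-target rule also uses 10 mm.
- **Methods (9.1.3).** There is no 15 mm rule here. Superficial lesions, with palpable nodes given as an example, are measurable at 10 mm by calipers.
- **Analysis (10.4.1).** Response rates use the Section 9.0 criteria, are reported separately for solid tumor and cHL by treatment, and include de-escalation participants at any dose level.

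**The concern.** The same 12 mm node on CT is measurable for entry and non-measurable for response. Section 3.0 allows no exceptions to eligibility and lets sites use that section as the signed checklist, so sites will apply 10 mm as written. The cross-reference does not correct this, because it leads to 9.1.3 and not to 9.1.2.

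At stake is the response rate, one of the two secondary objectives of the solid tumor expansion cohorts (1.2.2). A participant can take a place as having measurable disease and then fall outside the plan's own definition of evaluable for objective response. Section 10.4.1 does not say whether its denominator is all treated participants or only the response-evaluable ones, so such a participant has no defined place in the estimate.

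**Working it through.** **1. The plan's own figure.** Section 10.2 gives an exact 95% interval of 48% to 87% for the 24-participant solid tumor cohort. Clopper-Pearson limits at an ORR of 70% (x = 0.70 × 24 = 16.8) are 48.0% to 86.8%, which matches. A whole count of 17/24 gives 48.9% to 87.4%. The figure is not in dispute; it is where the denominator matters.

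**2. Which rule applies to a node-only participant (CT, 10 to under 15 mm).**

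| Step | Section | Result |
|---|---|---|
| Measurable for entry? | 3.1.3 | Yes |
| Measurable for response? | 9.1.2 | No |
| Target lesion available? | 9.1.2 | No |
| Evaluable for objective response? | 9.1.1 | No |
| How scored? | 9.1.1, Table 5 | Non-target: CR, non-CR/non-PD, PD or not evaluated; no PR |

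**3. Shrinkage needed for CR.** The node must fall below 10 mm, with no new lesions, no other persisting non-target disease, and any raised tumor marker normalized. From baseline short axis b, the fall must exceed b − 10 mm; at a reading of 9 mm the reduction is (b − 9)/b.

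| b (mm) | Fall needed | Reduction at 9 mm |
|---|---|---|
| 10 | >0 mm (1 mm in whole millimetres) | 10.0% |
| 11 | >1 mm | 18.2% |
| 12 | >2 mm | 25.0% |
| 13 | >3 mm | 30.8% |
| 14 | >4 mm | 35.7% |
| 15 | >5 mm | 40.0% |

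For comparison, PR on target lesions needs a 30% decrease. Any node below 10/0.7 = 14.3 mm can pass the CR size rule with less than that. At 15 mm the fall must exceed 5/15 = 33.3%, so the 15 mm threshold keeps CR harder to reach than PR.

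**4. Effect of one participant on the response rate.** Counting one participant as a responder rather than a non-responder moves the rate by 1/n: 1/24 = 4.2 points (for example 7/24 = 29.2% becomes 8/24 = 33.3%). Dropping that participant from the denominator moves it by no more than 1/n: 8/24 = 33.3% against 7/23 = 30.4% is 2.9 points. With six de-escalation participants pooled, n = 24 + 6 = 30 and 1/30 = 3.3 points. The combination cohort is given as 24 in Section 10.2 but 12 in the synopsis and Section 10.1.2; on 12 + 6 = 18 pooled participants the figure would be 1/18 = 5.6 points.

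**5. Effect on precision (assumed counts only).** If 0, 1, 2, 4 or 6 of 24 were not evaluable, the interval at an ORR of 70% would be 48.0–86.8%, 47.5–87.1%, 47.0–87.4%, 45.7–88.1% or 44.3–88.9%. The width goes from 38.7 to 44.6 points at the extreme.

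**The case against.** The strongest reply is that Section 9 governs scoring and is clear enough: 10.4.1 designates its criteria, 9.1.2 classifies the small node, and Table 5 provides a way to score it. Response is not the primary endpoint, and everyone treated remains evaluable for toxicity. All of this stands, and it limits the point to the secondary response rate. It does not remove the mismatch at entry or supply a denominator rule.

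A reader might infer more than the documents support:

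- **That a 10 mm node on CT may be made a target lesion, giving a target-lesion CR on 1 mm.** Doing so would breach 9.1.2. One millimetre is also the boundary case; a 14 mm node needs more than 4 mm. The small-shrinkage CR arises instead through Table 5. The caliper clause in 9.1.3 leaves some ambiguity for palpable nodes, which the fix addresses.
- **That every expansion cohort is affected.** HL is sent to 9.3, and cutaneous Kaposi sarcoma has its own entry note and response criteria (9.2).
- **That the response rate could move by 8 to 17 points.** This needs a cohort of 12 analyzed alone and one or two false responders in it. No such count is given, and 10.4.1 pools de-escalation participants.
- **That slice thickness is a second contradiction.** Appendix IX says "Section thickness must be based on institutional standards (e.g., from 5 to 8 mm", but 9.1.3, to which 3.1.3 does refer, already covers this: "If CT scans have slice thickness greater than 5 mm, the minimum size for a measurable lesion should be twice the slice thickness". An 8 mm section gives a 16 mm minimum.

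Confirmatory scans four weeks after a first response (8.5.7, 9.1) are some protection against a chance reading. They do not change how small the qualifying shrinkage can be, and the footnote to the confirmation column of Table 4 confines it to trials with response as the primary endpoint.

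**Conclusion.** Wrong as written, within a narrow scope. For solid tumor participants assessed by RECIST, 3.1.3 and 9.1.2 set different nodal thresholds, and nothing in the cross-reference reconciles them. A participant whose sole qualifying lesion is a node of 10 to under 15 mm is admitted as measurable, is not evaluable for objective response, and can be scored only as non-target disease.

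The effect is on the secondary response rate alone; the DLT and MTD conclusions do not change. Each such participant is worth at most 4.2 points on 24, and 3.3 points on 30 after pooling. This assumes the cohort size of 24 in Section 10.2 and one six-participant de-escalation cohort. The number affected is not in the documents and may be zero, so no total bias can be stated.

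**What to change.** 1. **3.1.3.** State that, for participants other than those with HL, a nodal lesion must be at least 15 mm in short axis by CT (Section 9.1.2). Leave HL under 9.3 and Kaposi sarcoma under its own note. Add 9.1.2 to the cross-reference and keep 9.1.3, which holds the slice-thickness rule.
2. **9.1.3.** Align the palpable-node caliper wording with 9.1.2 so that one nodal threshold applies.
3. **10.4.1.** State whether participants already enrolled solely on nodes of 10 to under 15 mm are in the response-rate denominator, and report the rate with and without them. Sending them to Table 5 is not enough, because a 10 mm node read at 9 mm can still be a CR there.
4. **Appendix IX (optional).** Cross-refer the section-thickness range to the doubling rule in 9.1.3. This is a consistency edit, not the correction of a separate error.

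The cost is protocol wording and one sensitivity analysis. The downside is that some solid tumor patients, probably few, whose only disease is nodes of 10 to 14 mm become ineligible.

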- 3.1.10 CD4 Counts: For Stratum 1: CD4+ cell count greater than 200 cells/mm³ obtained within 2 weeks prior to enrollment at any U.S. laboratory that has a clinical laboratory improvement amendments (CLIA) certification or its equivalent.

For Stratum 2: CD4 cell count between 100-200 cells/mm³ obtained within 2 weeks prior to enrollment at any U.S. laboratory that has a CLIA certification or its equivalent.

Expansion Cohort: CD4 cell count for this cohort will be specified once Stratum 1 and Stratum 2 have completed enrollment (Section 3.3).

Solid Tumor Expansion Cohort: CD4+ cell count greater than 200 cells/mm³ obtained within 2 weeks prior to enrollment at any U.S. laboratory that has a CLIA certification or its equivalent.

cHL Cohort: CD4 cell count of at least 100 cells/mm³.

- 3.1.11 Participants must be PPD negative. Alternatively, the QuantiFERON-TB Gold In-Tube (QFT-GIT) assay (Cellestis Limited, Carnegie, Australia) can be used. An individual is considered positive for *M. tuberculosis* infection if the IFN- γ response to TB antigens is above the test cut-off (after subtracting the background IFN- γ response in the negative control). The result must be obtained within 12 weeks prior to enrollment. PPD positive (or Quantiferon assay positive) participants are permitted if prophylaxis has been completed prior to enrollment.
- 3.1.12 The effects of nivolumab and ipilimumab on the developing human fetus are unknown. For this reason and because other therapeutic agents used in this trial are known to be teratogenic, women of childbearing potential (WOCBP)¹ and men must agree to use adequate contraception (hormonal or barrier method of birth control; abstinence) prior to study entry and for the duration of study participation. WOCBP should use an adequate method to avoid pregnancy for 6 months) after the last dose of investigational drug. WOCBP must have a negative serum or urine pregnancy test (minimum sensitivity 25 IU/L or equivalent units of HCG) within 72 hours prior to enrollment and the start of nivolumab. Women must not be breastfeeding. Men who are sexually active with WOCBP must use any contraceptive method with a failure rate of less than 1% per year. Men receiving

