¹ Note: Women of childbearing potential (WOCBP) is defined as any female who has experienced menarche and who has not undergone surgical sterilization (hysterectomy or bilateral oophorectomy) or who is not postmenopausal. Menopause is defined clinically as 12 months of amenorrhea in a woman over 45 in the absence of other biological or physiological causes. In addition, women under the age of 55 must have a documented serum follicle stimulating hormone (FSH) level less than 40 mIU/mL.

nivolumab and who are sexually active with WOCBP will be instructed to adhere to contraception for a period of 31 weeks after the last dose of investigational product. Women who are not of childbearing potential (*i.e.*, who are postmenopausal or surgically sterile as well as azoospermic men) do not require contraception.

WOCBP receiving nivolumab will be instructed to adhere to contraception for a period of 6 months after the last dose of investigational product. Men receiving nivolumab and who are sexually active with WOCBP will be instructed to adhere to contraception for a period of 31 weeks after the last dose of investigational product.

Should a woman become pregnant or suspect she is pregnant while she or her partner is participating in this study, she (or the participating partner) should inform the treating physician immediately.

- 3.1.13 Participants MUST receive appropriate care and treatment for HIV infection, including antiretroviral medications when clinically indicated, and should be under the care of a physician experienced in HIV management. Participants will be eligible regardless of antiretroviral medication (including no antiretroviral medication) provided there is no intention to initiate therapy, or the regimen has been stable for at least 4 weeks with no intention to change the regimen within 12 weeks following enrollment.
- ____ 3.1.14 Participants who have Hepatitis C (both reactive anti-HCV antibody and detectable HCV RNA) and Hepatitis B (HBsAg positive and anti-HBc-Total positive), may be enrolled, provided total bilirubin is ≤1.5× institutional ULN, AST (SGOT) and ALT (SGPT) must be ≤3 X institutional upper limit of normal, and HBV DNA < 100 IU/mL (if Hepatitis B positive) within 2 weeks prior to enrollment.
 - 3.1.14 Ability to understand and to sign a written informed consent document.

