Ipilimumab can cause inflammation of endocrine organs including thyroid (Hashimoto's thryroiditis with positive antibodies) and adrenal glands, hypophysitis, hypopituitarism, and resulting thyroid and adrenal insufficiency, low ADH, prolactin, FSH, LH. Hyperthyroid with Graves' disease and positive antibody has been reported. Participants may present with subtle and nonspecific symptoms. The most common clinical presentation includes headache and fatigue. Symptoms may also include visual field defects, behavioral changes, and electrolyte disturbances including hyponatremia and hypotension. Adrenal crisis as a cause of the participant's symptoms should be excluded. Based on the available data with known outcome, most of the participants symptomatically improved with hormone replacement therapy. Long term hormone replacement therapy with HC

and synthroid will typically be required for participants developing hypophysitis/hypopituitarism after treatment with ipilimumab. Some participants have regained partial function following steroid treatment.

Monitor participants for clinical signs and symptoms of hypophysitis, adrenal insufficiency (including adrenal crisis), and hyper- or hypothyroidism. Headache is often the first symptoms of hypophysitis. Participants may present with fatigue, headache, mental status changes, loss of libido, abdominal pain, unusual bowel habits, and hypotension, or nonspecific symptoms, which may resemble other causes such as brain metastasis or underlying disease. Unless an alternate etiology has been identified, signs or symptoms of endocrinopathies should be considered immune-mediated and drug withheld pending evaluation. Participants may demonstrate both central (hypophysitis) and peripheral adrenal and thyroid insufficiency. Evaluation of hypophysitis should include pituitary MRI.

Endocrine evaluation, including TSH, should be performed at baseline prior to initial treatment

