8.5.1 Review of medical history since last visit

- 8.5.2 Physical examination (vital signs, weight, performance status)
- 8.5.3 Review of changes in concurrent medications
- 8.5.4 Laboratory studies (as defined in Section 8.1.5)
 - a) CBC with differential and platelet count within 2 days prior to treatment
 - b) Serum chemistries (odd # cycles only 5, 7, 9, etc.)
 - c) Serum amylase and lipase (odd # cycles only 5, 7, 9, etc.)
 - d) Serum or urine pregnancy test for WOCBP at Cycle 5 Day 1 and every 12 weeks thereafter
 - e) HIV viral load and CD4/CD8 count at Cycle 5 Day 1 and every 12 weeks thereafter: Viral load studies will be performed using an assay with a limit of detection of 75 copies/ml or less. Repeat Hepatitis B antigen and/or Hepatitis C antibody if positive at baseline.
 - f) Immunologic labs at Cycle 5 Day 1 and every 12 weeks thereafter after consisting of: rheumatoid factor, C-reactive protein, ANA, SPEP, immunoglobulins, and free light chains (FLC).
 - g) Endocrine labs at Cycle 5 Day 1 and every 12 weeks thereafter consisting of: TSH, free T4, TPO, morning ACTH, and morning cortisol if ACTH is abnormal
- 8.5.5 AE assessment
- 8.5.6 Biological sample submissions for correlative studies. Samples will be collected as defined in Section 8.1.10, unless otherwise noted.
 - a) Collect two 6 ml red top tubes for assessment of circulating levels of proinflammatory molecules before cycle 5. Collection, shipping, and storage methods are described in Appendix XV.
 - b) Collect 2x2 mm biopsies in RNALater and formalin before cycle 5 as described in Appendix XIV (optional for KS cases only, with participant consent).
 - c) Collect anal swabs before cycle 5 as described in Appendix XVII (optional for anal cancer cases only, with participant consent).

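### The FSH condition in the menopause definition runs in the wrong direction for women over 45 and under 55, so it cannot confirm the status that lifts contraception and most pregnancy testing

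*Combined protocol and SAP*

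**What the plan says.** Section 3.1.12 ties contraception and pregnancy testing to childbearing potential, and footnote 1 defines that term. A WOCBP is "any female who has experienced menarche and who has not undergone surgical sterilization (hysterectomy or bilateral oophorectomy) or who is not postmenopausal". The footnote continues: "Menopause is defined clinically as 12 months of amenorrhea in a woman over 45 in the absence of other biological or physiological causes". The next sentence adds, as a further requirement, that "women under the age of 55 must have a documented serum follicle stimulating hormone (FSH) level less than 40 mIU/mL".

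Two consequences follow from the status.

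- **Contraception.** The text after the footnote says that women "who are postmenopausal or surgically sterile as well as azoospermic men) do not require contraception".
- **Pregnancy testing.** At entry, "WOCBP must have a negative serum or urine pregnancy test". On treatment, Section 8.5.4 asks for "Serum or urine pregnancy test for WOCBP at Cycle 5 Day 1 and every 12 weeks thereafter". Sections 8.2.4 (Cycle 1), 8.4.4 (Cycles 2-4), 8.6.4 (combination expansion cohort) and the discontinuation visit in Section 8.7 carry the same limit to WOCBP.

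No other section restates or corrects the FSH condition. FSH is not among the screening laboratory tests in Section 8.1.5, so sites have only this footnote to work from.

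**The concern.** The words that open the FSH sentence make it a further requirement on top of amenorrhea. The natural reading is a laboratory safeguard: below age 55, amenorrhea alone is not enough to call a woman postmenopausal. For that purpose the comparator is backwards. A woman whose ovaries still work would be expected to meet it, and a woman whose ovaries have stopped would be expected to fail it.

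Section 3.1.12 says the fetal effects of both drugs are unknown. The women at stake are therefore those who could still conceive but are recorded as postmenopausal, because the protocol then asks neither contraception nor repeat pregnancy tests of them. Section 3.0 allows no exceptions to eligibility criteria and lets sites use its text as the source checklist, so a site following the footnote exactly would apply the error.

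**Working it through.** No sample size, power or event count is involved. The check traces the definition through to its consequences.

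**Inputs**

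1. Clinical menopause: over 45, 12 months of amenorrhea, no other cause (footnote 1).
2. Extra condition under 55: documented FSH below 40 mIU/mL (footnote 1).
3. Postmenopausal women need no contraception (Section 3.1.12).
4. Entry and on-treatment pregnancy tests are written for WOCBP (Sections 3.1.12, 8.2.4, 8.4.4, 8.5.4, 8.6.4).
5. FSH rises when ovarian function ceases. This is general physiology and an assumption here: the documents give no menopausal FSH range.

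**Classification of a woman who is not surgically sterile, as written**

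| Woman | Status | Contraception and WOCBP-only tests |
|---|---|---|
| 45 or younger | WOCBP whatever her FSH | required |
| Over 45 and under 55, amenorrhea has another cause | WOCBP whatever her FSH | required |
| Over 45 and under 55, 12 months unexplained amenorrhea, FSH not documented | WOCBP | required |
| Same, FSH below 40 | postmenopausal | **not required** |
| Same, FSH 40 or above | WOCBP | required |
| 55 or older, 12 months unexplained amenorrhea | postmenopausal | not required |

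FSH changes the result only in the fourth and fifth rows. By input 5, the fourth row holds the women whose ovarian failure is least supported by the test, and they are released. The fifth row holds those for whom it is best supported, and they are retained.

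**Could the sentence mean something else?** If it described who *is* of childbearing potential, a 30-year-old without a documented FSH would fall outside the group, which cannot be intended. If it were a free-standing eligibility rule, every woman under 55 would need an FSH below 40 to enrol, which nothing else in Section 3 supports. Reading it as a qualifier on menopause is the only workable sense.

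**A second wording problem in the same footnote.** The WOCBP sentence joins its two exceptions with *or*. Taken literally, an unsterilised postmenopausal woman remains WOCBP because she meets the first limb. The contraception exemption shows this is not meant, and the table uses the intended reading. The two statements still conflict.

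**Does anything downstream catch the error?** In part. Footnote b to both schedules in Appendix I calls for a negative baseline pregnancy test within 72 hours of starting nivolumab and does not limit it to WOCBP. Footnote e gives the tests for Cycles 1 to 5 in a sentence that also omits the limit. Both conflict with the WOCBP-only wording of Section 8. Neither touches contraception.

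**The case against.** The strongest reply has four parts.

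- **The direction is not shown by the documents.** True: it rests on general physiology. A reader might take Section 5.2.3 as confirmation, since it lists "hypophysitis, hypopituitarism, and resulting thyroid and adrenal insufficiency, low ADH, prolactin, FSH, LH" among ipilimumab's endocrine effects. That passage describes toxicity on treatment and says nothing about menopausal status at screening, so it does not corroborate the point.
- **Part of the harm is already blocked.** A reader might infer that any potentially fertile woman under 55 with a low FSH loses protection. The text does not support that. She must also be over 45 and have 12 months of amenorrhea with no other cause, so recognised pituitary disease, for example, fails the earlier test. This narrows the group but does not repair the comparator.
- **Not every safeguard hangs on the definition.** The Appendix I footnotes can be read as a baseline test for all women, and the instruction to report a suspected pregnancy covers any woman on study. This stands. The release concerns contraception and the tests limited to WOCBP.
- **The size is unknown.** A reader might apply an assumed age share to the 32 planned women: 20% to 40% gives 0.20 × 32 = 6.4 to 0.40 × 32 = 12.8. That counts women in an age band, on an assumed share. It does not count women with 12 months of unexplained amenorrhea and FSH below 40, so it is not an estimate of those wrongly released.

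What survives is that the stated threshold misclassifies when followed, and no other section corrects it.

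**Conclusion.** The FSH sentence is wrong as written. It cannot confirm the menopause definition it qualifies, and within its narrow range it releases the women it should retain. The finding rests on FSH rising when ovarian function ceases, and on reading the sentence as a condition on menopause.

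The exposed group is women over 45 and under 55 with 12 months of otherwise unexplained amenorrhea and a documented FSH below 40. Its size cannot be derived from the documents and is likely small. The two errors are not equal: keeping a postmenopausal woman as WOCBP costs extra tests and contraception, whereas releasing a woman who could conceive removes protection. A single FSH value does not settle any individual's status, so the finding concerns the rule and does not show that each woman is misclassified. No endpoint or analysis is affected. This is most likely a drafting error, but it has a safety consequence and should be corrected.

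**What to change.** The sponsor should reconcile the direction of the FSH comparator in footnote 1 with the menopause definition it is meant to support. The threshold itself is a clinical matter for the sponsor, and none is proposed here. The same amendment should:

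- reconcile the *or* in the WOCBP definition with the statement exempting postmenopausal women from contraception;
- reconcile the pregnancy-test wording in Appendix I, footnotes b and e, with the WOCBP-only rules in Sections 3.1.12 and 8, so that it is clear who is tested at baseline and in Cycles 1 to 5;
- check whether the electronic eligibility checklist described in Section 3.5 carries the same FSH wording. The checklist is not in the documents, so this is unknown.

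The cost is a short amendment, which under Section 12.2 needs CTEP and IRB approval. The footnote already requires the FSH value, so correcting its direction adds no laboratory test. Some women would move into, and others out of, the group tested and asked to use contraception; the net change cannot be predicted from the documents.
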